#### IEC has taken following decisions for the study/trial;

Scientific issues, ethical issues and PID, CF were discussed.

The committee has given the following suggestions to the PI:

- 1. If the drug 'Melatonin' is indicated and approved for therapy, what is the beneficial outcome of this study?
- 2. Justify the use of placebo?
- 3. Mention the side-effects of the drug. Mention the provision of support and medical treatment for study related adverse side-effects.
- 4. The study involves 'evaluation of sleep abnormalities'. Include a psychiatrist in the study.
- 5. Mention source of healthy controls.
- 6. Mention method of randomization.
- 7. The study will require CTRI registration before start of study.
- 8. Submit properly framed separate PID's for controls, patients and legally accepted relative (LAR). Mnetion the collection of blood and stool also in the PID.
- 9. The departmental research committee meeting on 2/1/2019, however, the meeting minutes

## AN1-V1/SGSOP 03/V1

## Project Submission Form for Review by IEC

(6 copies and a CD required)

## A. Identification details:

*IEC Code No. ( To be filled by the Bioethics cell):
Study/Protocol No. (For drug/device trials/any other, to be filled by PI):
Type of project: Intramural [ ] Extramural [ ] Drug trial/device [ ] Independent [ ] MD/DM/MCh/PhD/SRF Project [ ] Collaborative [ ] Other [ ] Status of review: New [ ] Revised [ ] Proposal Title: Frequency of sleep abnormalities in patients with irritable bowel syndrome and its relationship with symptom severity, quality of life and effect of pharmacological intervention to improve sleep on these parameters

## B. Investigator details:

±±DT.	Name, Designation, Qualifications	Departmental Tel Nos. & Email ID	Signature
**PI	[name] [name], DM [name] SGPGI	CUG:[name] [name] Email: [contact]	ù (Gud
1.Co-PI	[name], Professor, Microbiology SGPGI	CUG:[name] [name] Email: [contact]	[name]

\*\*One page recent, signed and dated curriculum vitae of the investigators indicating qualifications and relevant experience for new or investigator outside SGPGI or of the student (MD/MS/DM/MCh/PhD) who has submitted thesis/project

C. Sponsor Information:	Applicable [ 🗸 ]	Not applicable []
1. Name of sponsor/CRO:	Will be submitted to UP C	ST for funding after Ethics clearance
2. Indian: a) Governme	ent Central S	tate Institutional
b) Private	]	
3. International: Governm	nent Private Private	UN Agencies
4. Industry: National	Multinational [	
5. Contact address of spo	nsor/CRO: Not applicable	
6. Budget: Rs. Provided		
7. Details of allocation of	budget in Clinical Trial A	greement: Yes [ ] No [ ] Not
applicable		
D. Study related Informat		
1. Design of study: Epide	miological Basic So	ciences Behavioral
l .		Centre Multicentre
2. No. of participants:	SGPGI	Total (if multicentre)
Patient*	97 9	7
Control*	97	97
3. Duration of study: Tv	vo years	
4. Duration of subject p	articipation (no. of visit by	a participant in study): Two
*Please mention samp	le size calculation and sour	ce of control in methodology
The related case-control s	tudies were reviewed for c	alculation of sample size. The frequency of
		6 and 43% whereas in control it has been
		average of these, we considered among IBS
		disorder is 40% and 22%, respectively,
considering a power of 8	0%, alpha value of 0.05 ar	nd ratio of case to control is 1:1. As per the
1		

calculation, we propose to include 97 cases and 97 controls.

For interventional study with melatonin and placebo, sample size was calculated based on the data that improvement occurred in 88% patients if treated with melatonin as compared to 47% with placebo (Lu WZ. APT 2005; 22: 927-934). Hence, 34 patients will be treated with melatonin and 34 with placebo (two sided CI 99%, power 80%, case:control 1:1, and p value <0.05). Considering 20-25% loss to follow-up, 97 patients with IBS will be randomized to melatonin and placebo.

E. Interventional study: Yes [ • ] No [ ]	If No, move to next section i.e.
NA	
1. Does the study involve use of	
Drugs Devices Vaccines	Radiopharmaceutical
Recombinant DNA/Gene therapy Stem cell Stem cell	(need BARC approval)
(need DBT- GEAC approval (NAC-SCRT registration and	d approval)
Indian Systems of Medicines/ Alternate systems of Medicine	
Any Other None None	
2. Is it approved and marketed	
In India UK & Europe USA O	ther Countries, Specify
3. Does it involve a change in use, dosage, route of administr	ration? Yes No
If yes, whether DCGI's/Any other Regulatory Authority's Permi	ssion is obtained?
	Yes No No
If yes, copy of permission attached.	Yes No No
4. Is it an Investigational New Drug?	Yes No No
If yes	
a. Investigator's Brochure enclosed	Yes No No
b. Preclinical studies data available (If yes, provide summary)	Yes No No
c. Clinical studies data available (If yes, provide summary)	Yes No No
d. Clinical study is Phase I Phase II Phase III	Phase IV NA NA
If phase I-III will the drug/device be provided free?	Yes
If phase IV will the drug/device be provided at cost less that	n Yes 🗌 No 🗌
Hospital pharmacy?	
e. DCGI's permission obtained	Yes No No
If yes, copy of letter enclosed	Yes
5. Data monitoring	
a. Is there a plan for reporting of adverse events?	Yes ✓ No No
If yes, reporting will be done to	Sponsor ☐ IEC ✓ ☐
b. Is there a plan for interim analysis of data?	Yes ✓ No No
6. Provision for travel/treatment due to injury out of study	Yes ✓ No No

If yes, by Sponsor ☐ Investigator ✓ ☐	Insurance Compan	y Any Other		
7. Registered with Clinical Trial Registry -	India	Yes No No		
If yes copy of certificate enclosed	Will be don	ne after Ethics clarance		
Yes No No				
F. Details of participant of study:				
1. Will subjects from both sexes be recruited	: Yes [ 🗸 ]	No [ ]		
2. Inclusion/exclusion criteria given:	Yes 🗸 [ ]	No [ ]		
3. Type of subjects:	Volunteers [ 🗸 ]	Patients [ • ]		
4. Vulnerable subjects	Yes [ ]	No[ •]		
( if Yes tick the appropriate boxes)				
Pregnant Women [ ] Children [ ]	Elderly [ ]	Fetus [ ]		
Illiterate [ ] Handicapped [ ]	Terminally ill [ ]	Seriously ill [ ]		
Mentally challenged [ ] Economically &	socially backward [ ]	Any other [ ]		
5. Special group subjects:	Yes [ ]	No[ ✓]		
( if Yes tick the appropriate boxes)				
Captives [ ] Institutionalized [ ]	Employees [ ]	Students [ ]		
Nurses/Dependent [ ] Staff [ ]	Armed Forces [ ]	Any Other [ ]		
G. Privacy and confidentiality:				
1. Study Involves Direct Identifiers (Pt. id	entified by name/Cr. no	o.)		
Indirect Identifiers/Code	d (Pt. identified after bro	eak of code)		
Completely Anonymised /Delinked (Pt. cannot identified)				
2. Confidential handling of data by staff		es v 🗆 No 🗆		

## H. Detail of sample collection (If no sample being collected, move to next section i.e. I):

A. Regarding sample collection		
1. Collection of organs or body fluids or blood. If yes, please spec	cify Yes 🔣	No 🗌
Type: Blood, urine, stool		
Amount each time_5ml Total_5 ml		
No. of time two		
2. Collection of fetal tissue or abortus. If yes, please specify	Yes	No 🔳
3. Use of pre-existing/stored/left over samples. If yes, please spec	eify Yes [	No ✓ □
4. Proper disposal of material	Yes ✓	No 🗌
B. Special situation		
1. Will any sample collected from the patients be sent abroad?	Yes 🗌	No ✔□
If yes, give details and address of collaborators		
	.	
a. Sample will be sent abroad because (Tick appropriate box)		
Facility not available in India		
Facility in India inaccessible		
Facility available but not being accessed		
If so, reasons		
b. Has necessary clearance been obtained	Yes	No 🗌
2. Collection for banking/future research	Yes	No 🗌

I.

## Participant Information Document (PID) and Consent Form:

1. Consent	*Written	✓ □	Oral		Audio-Visua	al 🔲
Patient Information documents and consent form attached: (Tick the included elements)						
Understandable	Understandable language   Alternatives to participation					→ □
Statement that s	tudy involves researc	h 🗸 🗌	Confid	lentiality	of records	→ □
Sponsor of study	у	√ □	Contac	et inform	ation 🗸 🗌	
Purpose and pro	cedures	→ □	Statem	ent that	consent is volu	ıntary 🗸 🗌
Risks & discom	forts	→ □	Right t	to withdr	aw	→ □
Benefits		→ □	Benef	īts if any	on future	→ □
Consent for futu	re use of material bio	ological []NA				
Free supply of d	rug till it is not marke	eted in country	if nece	ssary 🗌	NA	
Compensation for	or study related injury	y 🗌 🗸				
Translation of P	articipant Information	n Document (P	ID) in l	ocal Lan	guage 🗌	
2. If healthy v	olunteers, PID for th	hem			Yes √ [	]
3. If participa	nt is child, PID for p	parent			Yes	□ NA
4. PID and As	sent Form for child	8-18 yrs			Yes	□ NA
5. Consent for	m in English 🗸 🗌	Local 1	Languag	ges 🗸 🗌		
(For particip	ant/healthy volunteer	;)				
6. Who will ob	6. Who will obtain consent? PI-Co-PI ✓ ☐ Nurse/Counselor ✓ ☐					
Research Staff  Any Other						
*If written cons	ent is not obtained, g	give reasons				
NA	••••••	• • • • • • • • • • • • • • • • • • • •				
				<del>, ,</del>		
J. Will any ad	vertising be done for	r recruitment	of Subj	jects?	Yes	☐ No ■
(Posters, flye	ers, brochure, website	es – if so attach	а сору	·)		
						· · · · · · · · · · · · · · · · · · ·
K. For archiva	l of record by Bioetl	hics cell for m	ore Yes	s 🗸 🗌 N	lo Not ap	plicable 🗌
than 5 years	required					
If yes, for ho	w many years					
т						

## Risk and benefits:

1. Is there physical/social/psychological risk/discomfort?	Yes ✔ No 🗌		
If yes, Minimal or no risk			
More than minimum risk			
High risk			
2. Is there benefit a) to the subject?	Yes ✔□ No□		
Direct 🗸 🗌	Indirect		
b) to the society	Yes ✔☐ No ☐		
3. Do you think that the risk is in commensurate with the benefits to be accrued			
subjects/community/country?	Yes ✔☐ No ☐		
4. Please identify the ethical issues involved in your study: There is a	no ethical issue		
involved in our study.			
M. Do you have conflict of interest?	Yes ☐ No ✔☐		
(Financial/Non financial)			
If yes, specify			

### Brief proposal summary:

Irritable bowel syndrome (IBS), a common gastrointestinal (GI) disorder in India and in the rest of the World, is enigmatic in its pathogenesis. IBS is associated with recurrent abdominal pain or discomfort, bloating, incomplete evacuation, altered bowel habit, and abnormal stool forms (1, 2). The etiology of IBS remains unclear and different factors were thought to be involved like, genetics and environmental factors, visceral hypersensitivity, altered gut microbiota or disorder of the microbiota-gut-brain axis and various psychological factors like anxiety, depression, and insomnia or sleep disturbance (3). Due to increasing work pressure in today's society, and the consequent shift duty and psychological stress, the frequency of sleep disorders is increasing; disturbed sleep may be associated with a vicious cycle in which altered sleep may result in gastrointestinal (GI) disturbances, which in turn, may jeopardize sleep further. Disorder of the gut microbiota, the largest organ of the human body, is being suggested to be responsible for several GI and extra-GI diseases. Qualitative change in gut microbiota is currently studied by next generation sequencing. Gut and sleep patterns work in an axis - a two-way street of communication, some studies reported altered gut microbiota or dysbiosis modulates peripheral

and central nervous system function, leading to alterations in brain signaling and behavior that possibly leads to sleep disturbances (4).

Several case control and meta-analyses have reported an association between sleep disturbance and irritable bowel syndrome (IBS) as compared to healthy controls. However, the data regarding relationship between sleep disturbance and severity parameters of IBS have not been widely reported; moreover, interventions that improve disturbed sleep on these parameters are scanty. There is no systematic study on sleep disorders among patients with IBS from India.

Melatonin is a hormone made by the pineal gland; its biosynthesis is initiated by the uptake of the essential amino acid tryptophan and is an important inducer of sleep. Abnormality in melatonin has been shown in several studies on patients of IBS and functional constipation. A few studies also reported improvement in sleep and GI function after administration of melatonin. However, these studies had limitations due to small sample size, lack of randomization and inclusion of patients without sleep disorder. Moreover, there is no study from India on this issue (5,6,7).

Accordingly, we wish to undertake a study with the following aims:

- (i) Quality of sleep among patients with IBS and healthy controls.
- (ii) Levels of 6-Hydroxymelatonin sulphate (metabolite of melatonin) both in patients with IBS and healthy controls.
- (iii) Relationship between the IBS symptom severity (IBS-SSS), Health-Related Quality of Life (HRQL) and sleep disorder and melatonin deficiency,
- (iv) Relationship between gut dysbiosis and the above parameters
- (v) Effect of melatonin administration on IBS symptoms, HRQL and sleep.

Since sleep disturbance may be an important issue in IBS, the patients with IBS will be treated both with melatonin and standard treatment. Parameters like IBS-SSS, HRQL (8), Hospital Anxiety and Depression Scale (HADS) score (9), Pittsburgh Sleep Quality Index (PSQI) (10) will be studied in patients with IBS and healthy controls and these parameters would be repeated after 1 and 3 months follow-up in patients only. Urinary 6-Hydroxymelatonin sulphate will be studied in patients and controls before treatment with melatonin and it will be repeated after one month among patients with IBS only. Sleep study will be performed by PSQI questionnaire and also by polysomnography depending on the availability of the instrument. Study will analyse the effect of melatonin in GI and sleep disorder functions. Data will be analyzed using appropriate statistical techniques. P-values lesser than 0.05 will be considered significant.

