### Study protocol:

#### Sample size:

The related case-control studies were reviewed for calculation of sample size. The frequency of sleep disorder among IBS was observed to be 35% and 43% whereas in control it has been observed to be 29 and 14% respectively. Taking the average of these, we considered among IBS case and controls the average frequency of sleep disorder is 40% and 22%, respectively, considering a power of 80%, alpha value of 0.05 and ratio of case to control is 1:1. As per the calculation, we propose to include 97 cases and 97 controls.

For interventional study with melatonin and placebo, sample size was calculated based on the data that improvement occurred in 88% patients if treated with melatonin as compared to 47% with placebo (Lu WZ. APT 2005; 22: 927-934). Hence, 34 patients will be treated with melatonin and 34 with placebo (two sided CI 99%, power 80%, case:control 1:1, and p value

(3)

<0.05). Considering 20-25% loss to follow-up, 97 patients with IBS will be randomized to melatonin and placebo.

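### The protocol names no primary outcome or primary visit for melatonin versus placebo, and the improvement rates behind its 80% power are tied to no listed scale or visit

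*Protocol*

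**What the plan says.** The Brief proposal summary gives aim (v) as the "Effect of melatonin administration on IBS symptoms, HRQL and sleep", which is three unranked domains. It then lists the instruments: "Parameters like IBS-SSS, HRQL (8), Hospital Anxiety and Depression Scale (HADS) score (9), Pittsburgh Sleep Quality Index (PSQI) (10) will be studied". On timing it says that "these parameters would be repeated after 1 and 3 months follow-up in patients only". The analysis is described by "Study will analyse the effect of melatonin in GI and sleep disorder functions", and the significance rule is "P-values lesser than 0.05 will be considered significant". Nothing in the document ranks the scales or chooses between 1 and 3 months.

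The randomised comparison is sized in the Sample size section of the study protocol, and in the same words in section D of the Project Submission Form. The basis is that "improvement occurred in 88% patients if treated with melatonin as compared to 47% with placebo", taken from a cited trial. The result is 34 per arm, with the settings given as "two sided CI 99%, power 80%, case:control 1:1, and p value <0.05". Allowing for 20-25% loss to follow-up, 97 patients are to be randomised. The document does not say what improved, by how much, on which scale or at which visit.

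**The concern.** A trial that compares two arms needs one result, fixed in advance, that decides the comparison. Here any of several scales at either visit could be presented as decisive once the data are seen, and each would be consistent with the protocol.

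The sample size makes this more than an omission. It assumes a yes/no response, but the listed instruments are scored questionnaires and no responder cut-off is given for any of them. The 80% power therefore cannot be assigned to anything the trial says it will analyse, and the result finally reported as the main one may not be the one the trial was sized for.

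A second, smaller matter sits in the same sentence. A 99% two-sided confidence level and a P<0.05 threshold are both stated, and they imply different sample sizes and different power.

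**Working it through.** **Inputs from the protocol.** p1 = 0.88, p2 = 0.47, power 80%, 1:1 allocation, 34 per arm, 97 randomised, 20-25% loss (Sample size section). Three domains, two follow-up visits, threshold 0.05 (Brief proposal summary).

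**1. Reproducing 34 per arm.** Pooled-variance formula with d = p1 − p2 = 0.41 and p̄ = (0.88 + 0.47)/2 = 0.675:

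n = [z(1−α/2)·√(2p̄(1−p̄)) + z(0.80)·√(p1(1−p1) + p2(1−p2))]² / d²

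Continuity correction: n_c = (n/4)·[1 + √(1 + 4/(n·d))]²

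- α = 0.01 two-sided: n = (1.706 + 0.501)²/0.41² = 29.0; n_c = 33.7, so **34**. This is the protocol's figure.
- α = 0.05 two-sided: n = (1.298 + 0.501)²/0.41² = 19.3, so 20; n_c = 23.9, so 24.
- One-sided variants give 25 and 30 at 0.01, and 16 and 20 at 0.05 (without and with correction).

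Only two-sided 0.01 with continuity correction gives 34.

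**2. Power for 88% versus 47%** (continuity-corrected / Fisher exact). Evaluable patients: 97 × 0.80/2 = 38.8 and 97 × 0.75/2 = 36.4 per arm, taken as 38 and 36.

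| n per arm | α = 0.05 | α = 0.01 |
|---|---|---|
| 34 | 0.939 / 0.945 | 0.805 / 0.835 |
| 36 | 0.953 / 0.958 | 0.838 / 0.857 |
| 38 | 0.963 / 0.969 | 0.866 / 0.888 |

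**3. How far the power depends on the undefined outcome.** The protocol gives no alternative rates, so this is an illustration. With an assumed 75% versus 47% and 36-38 per arm, power is 59-63% at 0.05 and 35-39% at 0.01. If the outcome were a mean score, 34 per arm would have 80% power for a standardised difference of (z(1−α/2) + z(0.80))·√(2/34), which is 0.68 SD at 0.05 and 0.83 SD at 0.01. The protocol states no SD or target difference for any scale.

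**4. Chance of at least one false positive.** Assumption, not stated in the protocol: each domain of aim (v) is tested once at each visit at two-sided 0.05, and any significant result counts.

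- Six independent tests: 1 − 0.95⁶ = 26.5%. In melatonin's favour only: 1 − 0.975⁶ = 14.1%.
- Six tests with common correlation 0.3 to 0.7 (simulation): about 24% to 16%. In melatonin's favour only: about 12% to 8%.
- One test per domain, independent: 1 − 0.95³ = 14.3%. In melatonin's favour only: 1 − 0.975³ = 7.3%.

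**The case against.** The strongest reply is that multiplicity handling and detailed endpoint definitions are commonly left to a statistical analysis plan, which is not shown here. That stands for the choice of test and any multiplicity adjustment. It does not stand for the primary outcome, because the protocol already contains a sample size that depends on one. A later plan could choose an outcome, but could not show that 34 per arm was derived for it.

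It is also fair to say that the 26.5% is an upper bound. The same patients answer related scales twice, so independence is unlikely, and the protocol does not say that any one significant result would count as success.

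The 99% confidence level can be read as a cautious planning input alongside a single 0.05 testing rule. That reading is reasonable. What remains is that the 80% figure does not then describe the test to be done.

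Several stronger readings are tempting, and the document does not support them:

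- A reader might infer that no follow-up times are set. They are: 1 and 3 months. Only the choice between them is missing.
- A reader might infer that the trial is underpowered. On its own assumption it is not, at either alpha.
- A reader might infer that HRQL has been dropped, because the analysis sentence mentions only GI and sleep functions. That sentence is a loose summary, and HRQL is in aim (v) and among the repeated measures.
- A reader might take the form's visit count ("a participant in study): Two") as a contradiction of the schedule. It may refer to the two follow-ups. It needs clarifying, no more.

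**Conclusion.** The point holds. No primary outcome and no primary visit is named for the randomised comparison, and the 88% versus 47% behind the sample size is not connected to any listed scale or visit. The arithmetic for 34 per arm is sound, but its 80% power applies to an undefined response.

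If all three domains were tested at both visits, the false-positive chance would be about 16% to 26.5% depending on correlation, or about 8% to 14% counting only results in melatonin's favour. Both ranges rest on the assumed six-test reading.

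The alpha mismatch is secondary. The stated 80% corresponds to two-sided 0.01, while the stated rule of P<0.05 gives about 94-95% at 34 per arm. The visit count is minor. Overall this should be corrected, but it is not an error that invalidates the design.

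**What to change.** - Name one primary outcome at one of the two scheduled visits, as either a responder rule or a mean change.
- Justify the planning assumption for that outcome: two response rates, or a difference and an SD. Use 88% versus 47% only if improvement in the cited trial was measured in a matching way. This document alone cannot show that it was.
- State one alpha, and restate the power for the chosen outcome at about 36-38 evaluable per arm.
- Label all other scales and visits secondary or exploratory.
- Clarify how the visit count on the form fits baseline plus 1 and 3 months.

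The cost is protocol wording. Non-primary results will carry less weight. If 88% versus 47% can be justified, no extra patients are needed: power is about 84-89% at 0.01 and 95-97% at 0.05. If the justified difference is smaller, the restated power will be lower. With 47% on placebo and 36-38 per arm, 80% power (continuity-corrected) holds only down to about 80-81% on melatonin at 0.05, or 86-87% at 0.01.

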### Study protocol:

#### Sample size:

The related case-control studies were reviewed for calculation of sample size. The frequency of sleep disorder among IBS was observed to be 35% and 43% whereas in control it has been observed to be 29 and 14% respectively. Taking the average of these, we considered among IBS case and controls the average frequency of sleep disorder is 40% and 22%, respectively, considering a power of 80%, alpha value of 0.05 and ratio of case to control is 1:1. As per the calculation, we propose to include 97 cases and 97 controls.

For interventional study with melatonin and placebo, sample size was calculated based on the data that improvement occurred in 88% patients if treated with melatonin as compared to 47% with placebo (Lu WZ. APT 2005; 22: 927-934). Hence, 34 patients will be treated with melatonin and 34 with placebo (two sided CI 99%, power 80%, case:control 1:1, and p value

(3)

<0.05). Considering 20-25% loss to follow-up, 97 patients with IBS will be randomized to melatonin and placebo.

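### The case-control planning rate for IBS is given as an average of 35% and 43% but printed as 40% instead of 39%, and 97 per group does not follow from the printed rates (minor)

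*Protocol*

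**What the plan says.** The Sample size section of the protocol bases the case-control comparison on two earlier studies. The IBS rates were "observed to be 35% and 43% whereas in control it has been observed to be 29 and 14% respectively". The planning rates are then described as averages: "Taking the average of these, we considered among IBS case and controls the average frequency of sleep disorder is 40% and 22%, respectively". The design settings are "considering a power of 80%, alpha value of 0.05 and ratio of case to control is 1:1", and the result is "As per the calculation, we propose to include 97 cases and 97 controls".

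The project submission form (section D, Study related Information, under item 4) repeats the averaging step, the 40% and 22%, and the result: "calculation, we propose to include 97 cases and 97 controls".

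Neither place says whether the test is one- or two-sided for this comparison, which formula was used, or whether the average was weighted.

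**The concern.** Three things should agree: the cited rates, the averaging step with the rates it yields, and the sample size. They do not. The mean of 35 and 43 is 39, already a whole number, so rounding cannot turn it into 40. A reader who enters the printed 40% and 22% into a standard formula does not get 97 either.

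This calculation is the only justification given for the 97 + 97 case-control sample, which serves the first aim, comparing sleep quality between IBS patients and healthy controls. If the IBS rate is what the text says was averaged, the stated 80% power is too high.

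**Working it through.** **Inputs**, all from the Sample size section: IBS rates 35% and 43%; control rates 29% and 14%; printed planning rates 40% and 22%; power 80%; alpha 0.05; ratio 1:1; result 97 per group. A two-sided test is my assumption.

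**Averages (equal weights).**
- IBS: (35 + 43)/2 = 39%
- Controls: (29 + 14)/2 = 21.5%

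**Formula (pooled variance under the null, no continuity correction).** With p̄ = (p₁ + p₂)/2:

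n = [1.960·√(2p̄(1 − p̄)) + 0.8416·√(p₁(1 − p₁) + p₂(1 − p₂))]² / (p₁ − p₂)²

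The unpooled version is n = (1.960 + 0.8416)²·[p₁(1 − p₁) + p₂(1 − p₂)] / (p₁ − p₂)².

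**Reproducing the plan's 97, at 40% v 21.5%.** p̄ = 0.3075; the two square roots are 0.6526 and 0.6394; the difference is 0.185.

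n = [(1.960 × 0.6526 + 0.8416 × 0.6394)/0.185]² = (1.8172/0.185)² = 96.5, so 97.

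**At the printed pair, 40% v 22%.** p̄ = 0.31; square roots 0.6541 and 0.6416; difference 0.18.

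n = (1.8219/0.18)² = 102.4, so 103.

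**At the actual means, 39% v 21.5%.** p̄ = 0.3025; square roots 0.6496 and 0.6377; difference 0.175.

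n = (1.8099/0.175)² = 107.0, so 107.

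**Power with 97 per group (pooled).** Power = Φ{[(p₁ − p₂)·√97 − 1.960·√(2p̄(1 − p̄))] / √(p₁(1 − p₁) + p₂(1 − p₂))}. For 39% v 21.5% the argument is (0.175 × 9.849 − 1.960 × 0.6496)/0.6377 = 0.706, which gives 76.0%.

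| IBS v control | n per group, pooled / unpooled | Power at 97, pooled / unpooled |
|---|---|---|
| 40% v 21.5% | 97 / 94 | 80.2% / 81.3% |
| 40% v 22% (printed) | 103 / 100 | 77.8% / 78.9% |
| 39% v 21.5% (actual means) | 107 / 105 | 76.0% / 77.1% |
| 39% v 22% | 114 / 112 | 73.3% / 74.4% |

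**Other ways of reaching 97 from the printed pair.** At 40% v 22%, the continuity-corrected two-sided formula gives 114, the arcsine formula 102, a one-sided test 81, and a one-sided test with continuity correction 92. None gives 97.

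**Source of the gap (pooled).** Using 40% in place of 39% lowers n from 107 to 97, or 10 per group. Printing 22% in place of 21.5% would raise it from 97 to 103, or 6 per group.

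**Scale.** Taken singly, the two cited studies imply far more extreme results at 97 per group: about 14% power at 35% v 29%, and over 99% at 43% v 14%.

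**The case against.** The strongest objection is materiality. One percentage point in a planning rate is trivial beside the spread of the cited rates. The randomised part is also untouched: it is sized from 88% v 47% at 34 per arm, and 68 patients allowing for 20–25% loss come to 68/0.80 = 85 up to 68/0.75 ≈ 91, which 97 IBS patients cover. This stands, and it is why the point is minor.

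The average could be weighted. Weights of 3:5 on the two IBS rates do give 40% (0.375 × 35 + 0.625 × 43). But the same study weights put the controls at 0.375 × 29 + 0.625 × 14 = 19.6%, not 22%. No weights or study sizes are given, and 22% fits the rounded simple mean. Weighting therefore does not explain the printed pair.

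That 40% v 21.5% was the pair entered is an inference, since 21.5% is printed nowhere. Other routes come close: a control rate of 22% with an odds ratio of 2.4 (the printed pair gives 2.36) needs 96 unpooled or 99 pooled, and a one-sided, continuity-corrected calculation at 39% v 21.5% gives 96. Neither gives 97, and each needs an input or a one-sided test that the text does not state. The caution about origin is fair, but the finding does not depend on it: the simple mean is 39%, and the printed rates do not yield 97.

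**Conclusion.** The concern holds, as a minor error in the text. The IBS rate is one point above the average it is said to be, and 97 per group follows from neither the printed rates nor the true averages. Against the stated 80%, power with 97 per group falls short by about 1 to 2 points at the printed pair and 3 to 4 points at the actual means. The sample size is consistent with a correct calculation at 40% v 21.5%, so the 80% claim needs the higher IBS rate.

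The power figures assume a two-sided 0.05 test without continuity correction, and the means assume equal weights. The design does not need to change.

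**What to change.** Keep 97 cases and 97 controls. The investigators should confirm which rates, formula and sidedness were used, then correct the Sample size section and the matching text in the project submission form in one of two ways.

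1. Smallest edit, keeping 97 and 80%: *The control rate is the mean of the cited rates (21.5%). The IBS rate of 40% is a planning assumption, one point above the cited mean of 39%. With two-sided alpha 0.05, 80% power and a 1:1 ratio, 97 per group are required; at 39% v 21.5% the power is about 76%.*
2. Keeping the averages: *The means of the cited rates are 39% and 21.5%. With 97 per group and two-sided alpha 0.05, power is about 76%.*

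Option 1 is right only if 40% was a deliberate choice, which the document does not say. In either case print 21.5% with its decimal, because 39% v 22% would imply 114 per group and about 73% power at 97.

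The cost is two or three sentences in two places, with no extra participants and no change to design or conduct.

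### The melatonin–placebo sample size mixes two significance levels: at p<0.05, 34 per arm gives about 94–97% power rather than 80%, and 97 is not 68 adjusted for 20–25% loss

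*Protocol*

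**What the plan says.** The Protocol sizes the randomised comparison in the section Study protocol, Sample size. The assumed effect is that "improvement occurred in 88% patients if treated with melatonin as compared to 47"% on placebo. The resulting number and its inputs follow in one sentence: "Hence, 34 patients will be treated with melatonin and 34 with placebo (two sided CI 99%, power 80%, case:control 1:1, and p value" <0.05). The project submission form, part D (Study related Information), prints the same parenthesis unbroken: "two sided CI 99%, power 80%, case:control 1:1, and p value <0.05". The double entry is therefore not a product of the page break in the sample-size section.

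The significance rule for the analysis is in the brief proposal summary: "P-values lesser than 0.05 will be considered significant".

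The number to be randomised is then given as "Considering 20-25% loss to follow-up, 97 patients with IBS will be randomized to melatonin and placebo". The preceding paragraph, which sizes the case-control comparison, ends "As per the calculation, we propose to include 97 cases and 97 controls".

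**The concern.** A sample-size calculation has one type I error rate. Here the same parenthesis carries a two-sided 99% level (alpha 0.01) and p<0.05 (alpha 0.05), and the required number differs by about half between them. The reader cannot tell which level produced 34, nor whether the stated 80% power applies to the p<0.05 rule under which the result will be judged.

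The step from 68 to 97 is presented as an allowance for 20–25% loss, but it is too large for that.

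At stake is whether the number randomised to melatonin or placebo can be traced to its stated inputs. The ethics committee asked the investigator to justify the use of placebo, so the reasoning behind the number randomised should be open to checking.

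**Working it through.** **Inputs (Protocol, Sample size).** p1 = 0.88, p2 = 0.47, difference 0.41, allocation 1:1, power 80%. Significance level: 0.01 or 0.05, both stated. The p<0.05 rule comes from the brief proposal summary; it gives no sidedness and is taken here as two-sided.

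**Formula.** Pooled two-proportion normal approximation, with p̄ = (0.88 + 0.47)/2 = 0.675:

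n = [z(1−α/2)·√(2p̄(1−p̄)) + z(power)·√(p1(1−p1) + p2(1−p2))]² / 0.41²

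with √(2 × 0.675 × 0.325) = 0.6624, √(0.1056 + 0.2491) = 0.5956 and z(power) = 0.8416.

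Continuity correction: n_cc = (n/4)·[1 + √(1 + 4/(n × 0.41))]².

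**Reproducing the 34.**

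| Two-sided alpha | Calculation | n per arm | With continuity correction |
|---|---|---|---|
| 0.01 | (2.576 × 0.6624 + 0.8416 × 0.5956)² / 0.1681 | 28.99 → 29 | 33.7 → **34** |
| 0.05 | (1.960 × 0.6624 + 0.8416 × 0.5956)² / 0.1681 | 19.3 → 20 | 23.9 → 24 |

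The stated 34 is reproduced exactly at two-sided alpha 0.01 with continuity correction. Unpooled, arcsine and one-sided variants were also tried at both levels, and none gives 34. The correction is therefore an inference; the Protocol does not state it.

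**Power of the stated number.** Uncorrected power is Φ[(0.41 − z(1−α/2) × 0.6624/√n) / (0.5956/√n)]. For the corrected version, 0.41 is replaced by 0.41 − 1/n. Fisher power is the exact sum over all outcomes.

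| n per arm | Alpha | Uncorrected | Corrected | Fisher's exact |
|---|---|---|---|---|
| 34 | 0.01 | 87.5% | 80.5% | 83.5% |
| 34 | 0.05 | 96.7% | 93.9% | 94.5% |
| 36 | 0.05 | 97.4% | 95.3% | 95.8% |
| 39 | 0.05 | 98.3% | 96.8% | 97.0% |

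The 80% thus belongs to alpha 0.01. At the p<0.05 rule the same 34 per arm gives about 94–97%.

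**The loss adjustment.** The required total is 34 + 34 = 68.

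- 20% loss: 68/0.80 = 85.
- 25% loss: 68/0.75 = 90.7 → 91.
- Multiplying instead of dividing: 68 × 1.20 = 81.6 → 82, and 68 × 1.25 = 85.
- Loss that would justify 97: 1 − 68/97 = 29.9%.

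No form of the 20–25% adjustment gives 97.

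**What 97 actually provides.** 97 × 0.75 = 72.75 and 97 × 0.80 = 77.6 patients remain, about 36–39 per arm. At alpha 0.05 and 80% power, against 47% on placebo, these numbers detect a response rate of about 77–78% uncorrected (30–31 points) or 80–81% by Fisher's test (33–34 points). The Protocol assumes 41 points.

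**What the stated inputs need at alpha 0.05.** 40–48 completers, hence between 40/0.80 = 50 and 48/0.75 = 64 randomised.

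**The case against.** The strongest reply is that the per-arm number is not a miscalculation. It is exact at two-sided alpha 0.01 with continuity correction, and sizing at a stricter level than the testing level is a coherent, cautious choice. Likewise, the sentence on 97 could mean only that randomising all 97 enrolled patients leaves room for the expected loss, which it does: 72.75 exceeds 68. Both departures add power, and no patient number, test or decision rule changes. The power figures also assume a binary improvement outcome and particular tests, whereas the brief proposal summary names no test and lists score measures.

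Much of this stands. The direction is conservative, and 34 is right for the stricter level. The exact power depends on the test, so the decimals should not be over-read. But the Protocol does not say that it sized at 0.01 and will test at 0.05; it lists both as inputs to one calculation. Power at 0.05 exceeds 80% under every test considered. And reading 97 as merely accommodating the loss does not make it the result of a 20–25% allowance, which is how the sentence presents it.

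A further caution applies to any rewording. Attributing 97 to the case-control part explains where the number comes from, but does not validate it: the same uncorrected pooled formula for 40% v 22% at 80% power and alpha 0.05 gives 103 per group.

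**Conclusion.** The concern holds. The sample-size statement gives two incompatible significance levels. Under the Protocol's p<0.05 rule, the stated 34 per arm has about 94–97% power for 88% v 47%, not 80%. The number randomised exceeds the correctly inflated total by 6–12 patients (97 against 91 or 85).

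The trial is not underpowered on its own inputs; both discrepancies err towards more power and more patients. The damage is to the justification: a reader would believe that the trial has 80% power for a 41-point difference, when at p<0.05 it could detect a clearly smaller one. It should be corrected, but it does not threaten the validity of the comparison.

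The conclusion rests on a two-sided test of a binary improvement outcome and on the 88% and 47% rates, which come from a cited study and could not be checked. Two points are inferences: that a continuity correction was used, and that 97 was carried over from the case-control paragraph.

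**What to change.** State one alpha for the randomised comparison, consistent with the brief proposal summary, and use the same text in the Sample size section and in part D of the submission form. There are two ways to do it.

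1. **Size and test at 0.05.** Remove the 99% level and the 34-per-arm derivation, and write, for example: *Two-sided alpha 0.05. The 97 IBS patients, the number set for the case-control comparison, will be randomised. After 20–25% loss about 36–39 per arm remain, giving about 96–97% power by Fisher's exact test (97–98% uncorrected) for 88% v 47%.*
2. **Keep 34 per arm.** State that it was sized at two-sided alpha 0.01 with continuity correction, if the investigators confirm this, as a conservative choice with testing at 0.05. Add that 97 is the case-control number and covers up to about 30% loss.

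The second keeps what may have been the investigators' actual design choice; the first is simpler to read against the p<0.05 rule. Either costs only wording in two places and changes no patients or procedures.
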